10.2. Criteria for Potentially Clinically Significant Values (PCSV)

Parameter	Treatment Emergent PCSV	Comments
Clinical Chemistry		
ALT*	>3 and ≤ 5 ULN and baseline ≤ 3 ULN*	Enzyme activity must be expressed in ULN, not in IU/L.
	>5 and ≤ 10 ULN and baseline ≤ 5 ULN	FDA DILI Guidance July 2009.
	>10 and ≤ 20 ULN and baseline ≤ 10 ULN	Each category is calculated independently.
	>20 ULN and baseline ≤ 20 ULN	* At least one level is required, multiple levels are optional for phase 2/3 studies. If it is desirable to get the distribution across the different PCSV levels, additional shift table on ≤ 3 , >3 to ≤ 5 , > 5 to ≤ 10 , >10 to ≤ 20 , and > 20 category for baseline vs. post baseline may be provided

Parameter	Treatment Emergent PCSV	Comments
AST*	>3 and \leq 5 ULN and baseline \leq 3 ULN*	Enzyme activity must be expressed in ULN, not in IU/L.
	>5 and \leq 10 ULN and baseline \leq 5 ULN	FDA DILI Guidance July 2009.
	>10 and \leq 20 ULN and baseline \leq 10 ULN	Each category is calculated independently.
	>20 ULN and baseline \leq 20 ULN	* At least one level is required, multiple levels are optional for phase 2/3 studies. If it is desirable to get the distribution across the different PCSV levels, additional shift table on \leq 3, >3 to \leq 5, > 5 to \leq 10, >10 to \leq 20, and > 20 category for baseline vs. post baseline may be provided
Alkaline Phosphatase	>1.5 ULN and baseline \leq 1.5 ULN	Enzyme activity must be expressed in ULN, not in IU/L. FDA DILI Guidance July 2009.

Parameter	Treatment Emergent PCSV	Comments
Total Bilirubin*	
>1.5 and \leq 2 ULN and baseline \leq 1.5 ULN*
 
>2 ULN and baseline \leq 2.0 ULN
	
Must be expressed in ULN, not in μmol/L or mg/L. Categories are cumulative.
 
FDA DILI Guidance July 2009.
 
* At least one level is required, multiple levels are optional for phase 2/3 studies. If it is desirable to get the distribution of significant level, additional shift table on \leq1.5, >1.5 to \leq2.0 and > 2.0 category for baseline vs. post baseline may be provided

ALT/AST and Total Bilirubin	
(ALT >3 ULN and TBILI>2 ULN) and baseline (ALT \leq3 ULN or TBILI \leq2 ULN)
 
(ALT >3 ULN and TBILI>1.5 ULN) and baseline (ALT \leq3 ULN or TBILI \leq1.5 ULN)
	
FDA DILI Guidance July 2009.

Parameter	Treatment Emergent PCSV	Comments
ALT/AST and Total Bilirubin and ALP	(ALT >3 ULN and TBILI >2 ULN and ALP < 2 ULN) and baseline (ALT <=3 ULN or TBILI <=2 ULN or ALP >=2 ULN) (AST >3 ULN and TBILI >2 ULN and ALP < 2 ULN) and baseline (AST <=3 ULN or TBILI <=2 ULN or ALP >=2 ULN)	FDA DILI Guidance July 2009.
CPK*	>3 and ≤ 10 ULN and baseline ≤ 3ULN* >10 ULN and baseline ≤ 10ULN	FDA Feb 2005. Am J Cardiol April 2006. Categories are cumulative. * At least one level is required, multiple levels are optional for phase 2/3 studies. If it is desirable to get the distribution of significant level, additional shift table on ≤3, >3 to ≤10, and > 10 category for baseline vs. post baseline may be provided
Creatinine	≥150 μmol/L (Adults) and baseline < 150 μmol/L >=30% change from baseline and <100% change from baseline ≥100% change from baseline	Benichou C., 1994. 3 independent criteria

Parameter	Treatment Emergent PCSV	Comments
Uric Acid		Harrison- Principles of internal Medicine 17 th Ed., 2008.
Hyperuricemia	>408 µmol/L and ≤408 µmol/L at baseline	Two independent criteria
Hypouricemia	<120 µmol/L and ≥ 120 µmol/L at baseline	
Blood Urea Nitrogen	≥17 mmol/L and <17 mmol/L at baseline	Two independent criteria
Chloride		Two independent criteria
Hypochloremia	<80 mmol/L and baseline ≥ 80 mmol/L	
Hyperchloremia	>115 mmol/L and baseline ≤ 115 mmol/L	
Sodium		Two independent criteria
Hyponatremia	≤129 mmol/L and baseline > 129 mmol/L	
Hypernatremia	≥160 mmol/L and baseline <160 mmol/L	
Potassium		FDA Feb 2005.
Hypokalemia	<3 mmol/L and baseline ≥ 3 mmol/L	Two independent criteria
Hyperkalemia	≥5.5 mmol/L and baseline <5.5 mmol/L	

Parameter	Treatment Emergent PCSV	Comments
Glucose		
Hypoglycaemia	(≤ 3.9 mmol/L and $< LLN$) and (> 3.9 mmol/L or $\geq LLN$) at baseline	ADA May 2005.
Hyperglycaemia	≥ 11.1 mmol/L (unfasted); ≥ 7 mmol/L (fasted) and < 11.1 mmol/L (unfasted); < 7 mmol/L (fasted) at baseline	ADA Jan 2008.
Albumin	≤ 25 g/L and > 25 g/L at baseline	
Hematology		
WBC	< 3.0 Giga/L and ≥ 3.0 Giga/L at baseline (Non-Black); < 2.0 Giga/L and ≥ 2.0 Giga/L at baseline (Black) ≥ 16.0 Giga/L and < 16 Giga/L at baseline	Increase in WBC: not relevant. To be interpreted only if no differential count available.
Lymphocytes	> 4.0 Giga/L and ≤ 4.0 Giga/L at baseline	

Parameter	Treatment Emergent PCSV	Comments
Neutrophils	<1.5 Giga/L and \geq 1.5 Giga/L at baseline (Non-Black); <1.0 Giga/L and \geq 1.0 Giga/L at baseline (Black)	International Consensus meeting on drug-induced blood cytopenias, 1991. FDA criteria.
Monocytes	>0.7 Giga/L \leq 0.7 Giga/L at baseline	
Basophils	>0.1 Giga/L \leq 0.1 Giga/L at baseline	
Eosinophils	(>0.5 Giga/L and >ULN) and (\leq 0.5 Giga/L or \leq ULN at baseline)	Harrison- Principles of internal Medicine 17 th Ed., 2008.
Hemoglobin	\leq 115 g/L and > 115 g/L at baseline for male; \leq 95 g/L and > 95 g/L at baseline for Female. \geq 185 g/L and <185 g/L at baseline for Male; \geq 165 g/L and < 165 g/L at baseline for Female Decrease from Baseline \geq 20 g/L	Three criteria are independent. Criteria based upon decrease from baseline are more relevant than based on absolute value. Other categories for decrease from baseline can be used (\geq 30 g/L, \geq 40 g/L, \geq 50 g/L).

Parameter	Treatment Emergent PCSV	Comments
Hematocrit	≤ 0.37 v/v and > 0.37 v/v at baseline for Male ; ≤ 0.32 v/v and > 0.32 v/v at baseline for Female ≥ 0.55 v/v and < 0.55 v/v at baseline for Male ; ≥ 0.5 v/v and < 0.5 v/v at baseline for Female	Two Criteria are independent
RBC	Female < 3 Tera/L and baseline ≥ 3 Tera/L ≥ 6 Tera/L and baseline < 6 Tera/L Male < 4 Tera/L and baseline ≥ 4 Tera/L ≥ 7 Tera/L and baseline < 7 Tera/L	Unless specifically required for particular drug development, the analysis is redundant with that of Hb. Otherwise, consider FDA criteria.
Platelets	< 100 Giga/L and ≥ 100 Giga/L at baseline ≥ 700 Giga/L and < 700 Giga/L at baseline	International Consensus meeting on drug-induced blood cytopenias, 1991. Two independent criteria
Urinalysis		
pH	≤ 4.6 and > 4.6 at baseline ≥ 8 and < 8 at baseline	Two independent criteria
Vital signs		

Parameter	Treatment Emergent PCSV	Comments
HR	≤ 50 bpm and decrease from baseline ≥ 20 bpm ≥ 120 bpm and increase from baseline ≥ 20 bpm	To be applied for all positions (including missing) except STANDING.
SBP	≤ 95 mmHg and decrease from baseline ≥ 20 mmHg ≥ 160 mmHg and increase from baseline ≥ 20 mmHg	To be applied for all positions (including missing) except STANDING.
DBP	≤ 45 mmHg and decrease from baseline ≥ 10 mmHg ≥ 110 mmHg and increase from baseline ≥ 10 mmHg	To be applied for all positions (including missing) except STANDING.
Orthostatic Hypotension	Su SBP < 160 mmHg - SBP St – Su $\leq - 20$ mmHg DBP St – Su $\leq - 10$ mmHg Su SBP ≥ 160 mmHg – SBP St – Su $\leq - 30$ mmHg DBP St – Su $\leq - 15$ mmHg	
Weight	$\geq 5\%$ increase from baseline $\geq 5\%$ decrease from baseline	FDA Feb 2007.

Parameter	Treatment Emergent PCSV	Comments
ECG		Ref.: CPMP 1997 guideline. ICH E14 2005
HR	≤ 50 bpm and decrease from baseline ≥ 20 bpm ≥ 120 bpm and increase from baseline ≥ 20 bpm	
PR	≥ 220 ms and increase from baseline ≥ 20 ms	
QRS	≥ 120 ms & < 120 ms at baseline	
QTc	Absolute values (ms) > 450 ms and baseline ≤ 450 ms > 480 ms and baseline ≤ 480 ms > 500 ms and ≤ 500 ms at baseline Increase from baseline Increase from baseline 30-60 ms Increase from baseline > 60 ms	To be applied to any kind of QT correction formula. $\Delta QTc > 60$ ms are the PCSA to be identified in individual subjects/patients listings.

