5.3.2.1. Reasons for Permanent Discontinuation of Study Drug

Study drug dosing will be permanently stopped in the event of:

- A patient developing clinically significant sensory and motor neurologic events confirmed by a neurologist's examination and graded by a neurologist as a modified neuropathy grade >2 according to the Common Terminology Criteria for Adverse Events (CTCAE) v.4 (study sites should use CTCAE v.4 criteria throughout the study for consistency)
- A patient developing new or worsening signs and symptoms indicative of carpal tunnel syndrome

- Evidence of pregnancy
- Continued noncompliance with protocol-defined maximum acetaminophen/paracetamol use after appropriate counseling
- AESI:
 - Adjudicated arthropathy, as described in [Section 7.4.1.1](#)
 - Autonomic dysfunction, as described in [Section 7.4.1.2](#)
- Hepatotoxicity: The US FDA provides general guidance for all investigational products for drug-induced liver injury. A copy of the guidance is provided in the study reference manual. This guidance provides criteria for withholding study drug if a patient develops signs and symptoms of hepatitis during a study that should be followed.
 - Study drug should be discontinued if:
 1. Total bilirubin (TBL) >2 x upper limit of normal (ULN) or international normalized ratio (INR) >1.5
 2. Alanine aminotransferase (ALT) or aspartate aminotransferase (AST) >3 x ULN
 3. No other cause for 1 and 2 is readily apparent

Other causes of ALT, AST, and TBL elevations can include alcoholic hepatitis, autoimmune hepatitis, non-alcoholic hepatitis, heritable diseases (Gilbert's Syndrome), heart failure, and viral hepatitis.

Study drug may be withheld in patients who do not meet criteria for permanently discontinuing study drug, until an alternative cause for drug-induced liver injury can be determined. The patient may be re-challenged if an alternative cause for elevated liver function tests is found and the liver function tests return to normal, but only after discussion with the sponsor.

- Any other medical need, as determined by the investigator

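### SAP 10.2 defines ALT and AST PCSV levels as capped bands and requires only one of them, so no single-analyte row counts every patient above 3 x ULN; the bilirubin and CPK rows contradict their own counting comment

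*SAP*

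**What the plan says.** SAP 10.2 gives ALT and AST the same four levels:

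- level 1: ">3 and ≤ 5 ULN and baseline ≤ 3 ULN"
- level 2: ">5 and ≤ 10 ULN and baseline ≤ 5 ULN"
- level 3: ">10 and ≤ 20 ULN and baseline ≤ 10 ULN"
- level 4: ">20 ULN and baseline ≤ 20 ULN"

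The counting comment for both enzymes is "Each category is calculated independently". A starred note on ALT, AST, total bilirubin and CPK reads "At least one level is required, multiple levels are optional for phase 2/3 studies". A shift table over the same bands is offered as a further option.

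Total bilirubin has two rows, >1.5 to 2 x ULN and >2 x ULN. CPK also has two, >3 to 10 x ULN and >10 x ULN. In both cases the first row has an upper limit, yet the comment is "Categories are cumulative".

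SAP 5.8.4 calls for PCSV summaries by period and does not say which levels they will show. SAP 5.8 uses all post-baseline values in the on-treatment period, scheduled and unscheduled. Protocol 9.5.3.2 promises a count and percentage of patients with a PCSV for each laboratory test.

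**The concern.** The proportion of patients with clinically significant laboratory changes is a stated safety objective (Protocol 2.3, SAP 1.1.3). The usual summary of transaminase rises is the number of patients in each arm above a threshold, starting here at 3 x ULN. A capped band does not give that number. A patient who moves from normal to well above 5 x ULN with no measured value in between drops out of the lowest band, so the row can get smaller as values get worse. If only one level is tabulated, as the note allows, nothing else in the single-analyte table need show that patient.

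For bilirubin and CPK, two programmers following the same appendix could produce different row 1 counts from the same data.

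**Working it through.** The plan states no figure to reproduce. The check applies the printed row definitions to assumed profiles.

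**ALT and AST.** A patient counts in a level with lower limit L and upper limit U if baseline ≤ L and any on-treatment value v satisfies L < v ≤ U; the top level has no U. The profiles are hypothetical, in multiples of ULN, with baseline 1.

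| Patient | Values | >3 to 5 | >5 to 10 | >10 to 20 | >20 | Above 3 |
|---|---|---|---|---|---|---|
| A | 4 | 1 | 0 | 0 | 0 | 1 |
| B | 8 | 0 | 1 | 0 | 0 | 1 |
| C | 4, 8 | 1 | 1 | 0 | 0 | 1 |
| D | 4, 12, 25 | 1 | 0 | 1 | 1 | 1 |
| E | 25 | 0 | 0 | 0 | 1 | 1 |
| F | 2 | 0 | 0 | 0 | 0 | 0 |
| Total | | 3 | 2 | 1 | 2 | 5 |

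- Level 1 alone gives 3 of the 5 patients above 3 x ULN. It misses B and E.
- No other level alone gives 5 either (2, 1 and 2).
- Adding the rows gives 3 + 2 + 1 + 2 = 8, because C is counted twice and D three times.

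**Ordering of arms.** Take one arm with five patients whose only raised values are 4, 6, 8, 12 and 25 x ULN, and another with two patients whose only raised value is 4 x ULN. Level 1 reports 1 and 2. The counts above 3 x ULN are 5 and 2. The arm with fewer and milder rises looks worse in level 1.

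**Can a band be skipped?** Chemistry is scheduled at weeks 4, 8, 12 and 16 during treatment (Protocol Table 1), so values can move a long way between samples. Protocol 6.3.3.10 requires significantly abnormal tests to be repeated, and a repeat may or may not fall between 3 and 5 x ULN. Whether a patient at 8 x ULN also enters level 1 then depends on when the samples were taken.

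**Bilirubin and CPK**, under each reading:

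| Value | Row 1 as a band | Row 1 if cumulative | Row 2 |
|---|---|---|---|
| Bilirubin 3 x ULN | 0 (3 is above 2) | 1 (3 is above 1.5) | 1 |
| CPK 15 x ULN | 0 (15 is above 10) | 1 (15 is above 3) | 1 |

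**With open thresholds** the six ALT profiles give >3: 5 (A to E); >5: 4 (B to E); >10: 2 (D, E); >20: 2 (D, E). The counts never rise with the threshold, and the first is the number wanted.

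**The case against.** A reader might infer that severe rises disappear for all four analytes. The documents do not support that. The top level of every analyte is open (ALT and AST >20, bilirubin >2, CPK >10 x ULN). On the cumulative reading, CPK row 1 is itself the count above 3 x ULN. For bilirubin, 3 x ULN is not a cut-off at all. By-visit summaries include the maximum (SAP 5.8.4), and out-of-range values are flagged in listings (Protocol 9.5.3.2).

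A reader might also infer that the tables cannot be matched to the limits in Protocol 5.3.2.1. That goes too far as well. The protocol's "Alanine aminotransferase (ALT) or aspartate aminotransferase (AST) >3 x ULN" applies jointly with a bilirubin or INR criterion and the absence of another cause. SAP 10.2 has unstarred joint rows with open limits: ALT >3 with raised bilirubin, and ALT or AST >3 with bilirubin >2 and ALP <2 x ULN. Its bilirubin >2 x ULN row matches the protocol's bilirubin limit. These rows do not count a transaminase rise without raised bilirubin.

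The best remaining defence is that all four listed levels are PCSV criteria. The bands leave no gap, so for a patient with baseline ≤3 x ULN, meeting any level is the same as exceeding 3 x ULN. Confirmed screening values above 2.5 x ULN are excluded (Protocol 4.2.2), so that covers nearly everyone. The per-test count in Protocol 9.5.3.2 would then be right. This holds if all levels are programmed and an any-level row is shown. The SAP asks for neither, and its note permits less. The note also does not say which single level is required; reading it as level 1 is an inference from the star. Whichever level is chosen, the table is incomplete.

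It is also fair that one patient appearing in several independent rows is not an error in itself. It matters here only because a reader might sum the bands to recover the missing total.

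**Conclusion.** The point holds as a reporting defect. For ALT and AST, a table that meets SAP 10.2 can omit isolated rises outside the level shown; no single-analyte row gives the number above 3 x ULN, and summing rows can overcount. For bilirubin and CPK the supportable finding is narrower: row and comment disagree, and omission from row 1 follows only on the band reading.

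The size cannot be estimated from the documents, which give no expected rates. The counts above (3 against 5, with a row sum of 8) illustrate the mechanism on assumed profiles. They also assume that patients B and E have no value between 3 and 5 x ULN while rising or recovering; any such value would put them in level 1. What is missing is a dependable by-arm count of isolated rises. This is worth correcting before lock because it bears on a stated safety objective and costs little.

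**What to change.** In SAP 10.2, for reporting only:

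- Replace the bands with open cumulative thresholds, each with its matching baseline condition (for example, >3 x ULN with baseline ≤3 x ULN): ALT and AST >3, >5, >10, >20 x ULN; total bilirubin >1.5, >2 x ULN; CPK >3, >10 x ULN.
- Require all levels.
- Delete the note allowing a single level, and the comments on independent and cumulative counting that conflict with the rows.
- Keep the shift table for any banded distribution that is wanted.

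The appendix already uses open limits for alkaline phosphatase (>1.5 x ULN) and absolute QTc (>450, >480, >500 ms), so this brings the four analytes into line. The cost is appendix wording and a change of operator in the PCSV program. It needs no new data and touches no rule for managing patients.

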5.8.4. Clinical Laboratory Measurements

A treatment-emergent Potential Clinically Significant abnormal value (PCSV) is a laboratory value that was normal or abnormal but not meeting PCSV criteria at Screening and Baseline but became abnormal and met PCSV criteria after treatment with study drug. PCSV summary will be constructed for on-treatment period, post-treatment period and overall during the study.

Baseline clinical laboratory analytes and change from Baseline in clinical laboratory analytes to each scheduled assessment time will be summarized with descriptive statistics. Summary statistics will include using the number of patients (n), mean, standard deviation, median, Q1, Q3, minimum, and maximum. Scatter plot of change scores from baseline of LBPI vs. Alkaline phosphatase will be plotted by treatment group and visit. Mean change from baseline in Alkaline phosphatase values along with standard error bars will be plotted over time by treatment group.

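### The ALT/AST-with-bilirubin row in SAP 10.2 has no AST condition, so some AST-driven cases with ALT ≤3 ULN fall in no combined liver category

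*SAP*

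**What the plan says.** The table of potentially clinically significant values in SAP 10.2 has two rows that combine a transaminase with bilirubin.

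- The two-way row is labelled "ALT/AST and Total Bilirubin". Its lines begin "ALT >3 ULN and TBILI>2 ULN) and baseline" and "ALT >3 ULN and TBILI>1.5 ULN) and baseline". The baseline clauses that follow also refer to ALT and bilirubin only.
- The three-way row adds ALP. It has one line for each enzyme: "ALT >3 ULN and TBILI >2 ULN and ALP < 2 ULN) and baseline" and "AST >3 ULN and TBILI >2 ULN and ALP < 2 ULN) and baseline".

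SAP 5.8.4 sets how these definitions are used: "PCSV summary will be constructed for on-treatment period, post-treatment period and overall during the study".

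In the protocol, the enzyme part of the hepatotoxicity criterion in section 5.3.2.1 reads "Alanine aminotransferase (ALT) or aspartate aminotransferase (AST) >3 x ULN". That criterion has no ALP condition.

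**The concern.** The label of the two-way row promises either enzyme, and its content delivers one. Nothing suggests a deliberate choice. The three-way row directly below pairs ALT with AST, protocol 5.3.2.1 treats the two enzymes alike, and so does exclusion criterion 20. Neither document gives a reason for leaving AST out.

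What is at stake is the number of patients shown with a raised transaminase and raised bilirubin together. Separate rows for AST and bilirubin cannot supply it, because they do not show whether the same patient is in both. A patient could meet the enzyme and bilirubin limits of protocol 5.3.2.1 through AST and still be absent from both combined counts. Paracetamol is allowed as rescue through week 16, so the liver tables will be read with some care.

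**Working it through.** The plan gives no figure to reproduce here. The check is a logical one.

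**Inputs.** The four conditions in the two combined rows of SAP 10.2, with a normal baseline so that every baseline clause is met. This is a reasonable simplification: exclusion criterion 20 bars confirmed ALT or AST >2.5 ULN at screening, and the baseline clauses of the two-way row need only the enzyme ≤3 ULN or bilirubin at or below its limit.

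**Conditions as written (multiples of ULN).**

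- Two-way, line 1: ALT >3 and bilirubin >2
- Two-way, line 2: ALT >3 and bilirubin >1.5
- Three-way, ALT line: ALT >3 and bilirubin >2 and ALP <2
- Three-way, AST line: AST >3 and bilirubin >2 and ALP <2

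**Grid.** ALT at 1 or 4, AST at 1 or 4, bilirubin at 1, 1.8 or 2.5, and ALP at 1, 1.8, 2 or 3. The patterns of interest have at least one enzyme >3 and bilirubin >1.5. That gives 3 enzyme patterns × 2 bilirubin levels × 4 ALP levels = 24.

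| Enzyme pattern | Bilirubin | ALP | Patterns | In neither combined row |
|---|---|---|---|---|
| ALT 4, AST 1 or 4 | 1.8 or 2.5 | any | 16 | 0 |
| ALT 1, AST 4 | 2.5 | <2 | 2 | 0 |
| ALT 1, AST 4 | 2.5 | ≥2 | 2 | 2 |
| ALT 1, AST 4 | 1.8 | any | 4 | 4 |
| Total | | | 24 | 6 |

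All 6 uncounted patterns have AST >3 ULN with ALT ≤3 ULN. The mirror case shows the asymmetry: ALT 4, AST 1, bilirubin 2.5, ALP 3 is flagged by both two-way lines. Exchange the two enzyme values and nothing flags it. With both enzymes at 4, bilirubin 2.5 and ALP 3, the patient is flagged through ALT.

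The two-way row on its own omits all 8 AST-only patterns (2 + 2 + 4). The three-way row recovers only the 2 with bilirubin >2 and ALP <2.

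**After the change.** With AST lines parallel to the two ALT lines added to the two-way row, 0 of 24 patterns are uncounted.

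**The case against.** The strongest reply is that little is lost. A patient with raised AST and bilirubin is counted in the single-parameter AST and bilirubin rows, and in the ALP row when ALP exceeds 1.5 ULN. Out-of-range laboratory values are flagged in listings (protocol 9.5.3.2), and safety listings cover all periods (SAP 5.8). Significantly abnormal tests must be repeated and, if unresolved or unexplained, taken to the medical monitor (protocol 6.3.3.10). The table is also descriptive and does not claim to reproduce protocol 5.3.2.1, which is a rule for individual patients with an INR alternative and a condition that no other cause is apparent. All of this stands. It limits the consequence to the joint count but does not restore that count.

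Three stronger readings are tempting, and the documents do not support them.

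- A reader might infer that every AST rise with raised bilirubin and ALP ≥2 ULN is missed. It is missed only when ALT is ≤3 ULN.
- A reader might infer that AST plays no part in combined liver screening, or that the patient disappears from the safety tables. The three-way row has an AST line, and the single-parameter rows remain.
- A reader might take 6 of 24 as a rate, or attach a case number to the 563 randomized patients. The grid counts patterns, and the documents give no incidence.

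Finally, the row stands at a page break of the table, so an AST line lost from the public copy cannot be fully excluded. Both lines that are present are complete, and the neighbouring row kept its AST line, so this is unlikely. The sponsor can settle it from the source table.

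**Conclusion.** The row is wrong as written: its label and its conditions disagree, and a programmer who follows the conditions will produce a combined count that omits AST-only cases. The omission from every combined category is confined to AST >3 ULN with ALT ≤3 ULN, and then only with bilirubin >2 ULN and ALP ≥2 ULN, or with bilirubin >1.5 to ≤2 ULN at any ALP. That few patients will fall there is an assumption. The point is minor. It bears on no efficacy result, error rate or patient-management rule. The conclusion rests on the table text being complete and on baseline values that meet the baseline clauses.

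**What to change.** Add two separate AST lines to the two-way row in SAP 10.2:

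- `AST >3 ULN and TBILI >2 ULN`, with baseline `AST ≤3 ULN or TBILI ≤2 ULN`
- `AST >3 ULN and TBILI >1.5 ULN`, with baseline `AST ≤3 ULN or TBILI ≤1.5 ULN`

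Separate lines are better than one pooled ALT-or-AST condition. With a pooled condition the baseline clause is ambiguous when one enzyme is already high at baseline. Enzyme-specific lines avoid this and follow the pattern of the next row. If leaving AST out was intended, the alternative is to relabel the row as ALT only and give the reason.

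The cost is two added lines in the appendix table and the matching program code. AST is already in the chemistry panel (protocol 6.3.3.10), so no new data are needed.
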